7.3 Sampling

7.3.1 Sample size

We estimated the sample size using the free online software GRANMO, and the setting for two independent proportions.

In the view of the literature published so far, the proportion of reintubation in preterm newborns that are on invasive mechanical ventilation is 16% (studies differ between 12% and 20%, an average has been made).(62,63)

Accepting an alpha risk of 0.05 and a beta risk of 0.2 in a two-sided test, **271** subjects are necessary in first group and **271** in the second to recognize as statistically significant a difference greater than or equal to 0.1 percent units. A proportion in one of both groups has been estimated to be 16%. It has been anticipated a drop-out rate of 5% (0,05).

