 - **Chorioamnionitis:** it is a *dichotomous qualitative nominal variable*. It will be expressed as yes or no.
 - **Premature rupture of membranes** it is a *dichotomous qualitative nominal variable*. It will be expressed as yes or no.
 - **Maternal age:** it is a *continuous quantitative variable*. Measured in years
 - **Maternal size:** it is a *continuous quantitative variable*. Measured in cm.
 - **Cervical surgery:** it is a *dichotomous qualitative nominal variable*. It will be expressed as yes or no.
 - **Congenital uterine anomaly:** it is a *dichotomous qualitative nominal variable*. It will be expressed as yes or no.
 - **Diabetes or gestational diabetes:** it is a *dichotomous qualitative nominal variable*. It will be expressed as yes or no.
 - **Sexually transmitted infection:** it is a *dichotomous qualitative nominal variable*. It will be expressed as yes or no.

- **Smoking during pregnancy:** it is a *dichotomous qualitative nominal variable*. It will be expressed as yes or no.
- **Consuming alcohol or other toxics during pregnancy:** it is a *dichotomous qualitative nominal variable*. It will be expressed as yes or no.
- **Short intragestational period:** it is a *dichotomous qualitative nominal variable*. It will be expressed as yes or no.
- **Extrauterine infection:** it is a *dichotomous qualitative nominal variable*. It will be expressed as yes or no.

All these covariates will be obtained from the clinical history of the mother and the newborn, as all these information will be obtained before the recruitment of the patient in the study. Special importance will be given to the gynaecological clinical history of the pregnancy.

Table 4 - Summary table of variable

	Variable	Type of data	Categories or values
Independent variable	Protocol of invasive mechanical ventilation	Dichotomous qualitative nominal	PSV / ACVGV
Dependent variables	Number of reintubations	Discrete quantitative	Numerical
	Time of weaning	Continuous quantitative	Numerical (days)
Covariates	Sex	Dichotomous qualitative nominal	Men / Women
	Type of preterm	Dichotomous qualitative ordinal	Extremely preterm / Very preterm
	Birthweight	Continuous quantitative	Numerical (grams)
	CPR after birth	Dichotomous qualitative nominal	Yes / No
	5-minute Apgar score	Polychotomous qualitative ordinal	0-3 / 4-6 / 7-10
	Risk factors of prematurity		
	Previous preterm birth	Dichotomous qualitative nominal	Yes / No
	Second trimester miscarriage	Dichotomous qualitative nominal	Yes / No

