7.5 Study intervention

In this study there will be two different protocols applied for weaning of invasive mechanical ventilation in extremely and very preterm newborns with NRDS: PSV and ACVGV. These protocols will be applied by professional neonatologists.

When an extremely or very preterm newborn is in invasive mechanical ventilation due to NRDS and meets all inclusion criteria and any exclusion criteria, an informative document (see Annex 4) and an informed consent (see Annex 5) will be given to the parents or legal guardians to sign.

Once the newborn enters the study, the neonatologists will wait until this patient meets the **criteria to start the weaning**. These criteria will be **precisely explained** in the document given to all hospital coordinators during the formation sessions. The weaning criteria are the following:

- Clinical criteria:
 - o Stable patient
 - o No intercurrent process that may hinder weaning

- Respirator parameters
 - o $FiO_2 < 40$ mmHg
 - o $PEEP < 7$ cmH₂O
 - o $RR < 50$ rpm
 - o $PIP < 20$ cmH₂O

When the patient meets the weaning criteria, the intervention will start. The intervention will be carried out by a neonatology expert. The patient will be randomly assigned in one of the two groups:

- o Group 1: The protocol used for the weaning will be **pressure support ventilation (PSV)**

- o Group 2: The protocol used for the weaning will be **assist control volume guarantee ventilation (ACVGV)**

Both protocols of weaning have been properly explained in section 3.3.3 *Invasive mechanical ventilation*.

The patient will remain in weaning until he or she meets the **criteria for extubation**. These criteria will be **precisely explained** in the document given to all hospital coordinators during the formation sessions. The patient will be extubated to a CPAP with a nasal PEEP of 6 mmHg. The extubation criteria are the following:

- Gasometrical criteria:
 - o pH > 7,3
 - o pCO₂ < 50 mmHg
 - o pO₂ > 70 mmHg
 - o Sat Hb 90-95% (haemoglobin saturation)

- Clinical criteria:
 - o Stable patient
 - o Without active infectious process
 - o Without hemodynamically significant ductus
 - o Neurologically capable of maintaining a patent airway

- Respirator parameters:
 - o PEEP < 6 mmHg
 - o FiO₂ < 30 cmH₂O
 - o RR < 20 rpm
 - o PIP < 20 cmH₂O
 - o Tidal volume 5 ml/kg

[figure not shown]

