8.3 Multivariate interference

It will be necessary to do a multivariate analysis adjusting the covariates according to the independent variable with the dependent variables that can interfere in the results, to avoid possible confusion.

Poisson regression model will be used for the association between the intervention and the number of reintubations, which is a **discrete quantitative variable**.

Cox regression models will be used for the association of the intervention with the **time** of weaning, which is a **continuous quantitative variable**. It is calculated as a survival analysis.

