Annex 7 – Data form

ETIQUETA
IDENTIFICATIVA

DATA FORM

En relació amb el pacient

Setmanes de gestació	
Tipo de preterme	
Per al néixer	
Sexe	
CPR després de néixer	
Apgar score als 5 minuts	

En relació amb la mare

Part preterme previ	
Avortament del segon trimestre	
Edat	
Alçada	
Cirurgia cervical prèvia	
Anomalia uterina congènita	
Diabetis pregestacional	
Malaltia de transmissió sexual	
Fumadora	
Consum alcohol o altres tòxics	
Període intragestacional curt	
Infecció extrauterina	

En relació amb l'embaràs

Embaràs múltiple	
Corioamnionitis	
Ruptura prematura de membranes	
Diabetis gestacional	

En relació amb la intervenció

Codi del protocol utilitzat	
Reintubació	
Temps de weaning (en dies)

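### Ventilator settings and age at randomisation are not captured as trial data, so the Cox model for weaning time cannot adjust for each infant's starting status, at a possible cost in power on this secondary endpoint

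*Combined protocol and SAP*

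**What the plan says.** **Time zero.** Section 7.5 enrols the infant on the ventilator and then waits for the weaning criteria. "When the patient meets the weaning criteria, the intervention will start", and the infant is allocated to PSV or ACVGV. Section 10.3 (Stage 3) repeats this order. The criteria include limits on FiO2, PEEP, RR and PIP, so all four have to be checked on every infant at randomisation.

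**Endpoint.** Weaning time, the secondary outcome in Section 7.4, runs from the start of weaning to extubation. The extubation list in Section 7.5 sets limits on the same four settings, together with tidal volume, blood-gas and clinical criteria.

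**Data.** Table 4 lists 20 covariates: type of preterm, birthweight, sex, CPR, 5-minute Apgar and 15 maternal or pregnancy risk factors. On their source, Section 7.4 says "All these covariates will be obtained from the clinical history of the mother and the newborn" and places this before recruitment. Section 7.7 equates baseline data with these covariates. The intervention block of Annex 7 holds a protocol code, reintubation and "Temps de weaning (en dies" (weaning time in days). No ventilator setting and no age at randomisation appears in either place.

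**Analysis.** Section 8.3 states "Cox regression models will be used for the association of the intervention with the" time of weaning. Section 12.1 says the multivariate analysis will include the defined covariates. Sections 8.1 and 8.2 describe those covariates and compare them by protocol.

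**The concern.** The adjusted model for weaning time can use maternal height or cervical surgery, but not how much support the infant needed when the clock started. If starting support predicts time to extubation, two things follow. The Cox estimate of the treatment effect is attenuated and its test loses power. The baseline comparison also cannot show whether the arms began weaning in a similar ventilatory state, which is of interest because Section 12.1 blinds only the statistician and not the treating team. The values are already read at the bedside, so the information is lost to the analysis for want of a form field.

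**Working it through.** **1. The two lists of limits in Section 7.5, as printed.**

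| Setting | Start of weaning | Extubation | Comparison as printed |
|---|---|---|---|
| RR | < 50 rpm | < 20 rpm | limit is lower at extubation |
| PIP | < 20 cmH2O | < 20 cmH2O | same limit |
| PEEP | < 7 cmH2O | < 6 mmHg | units differ; 6 mmHg is about 8.2 cmH2O, so the printed extubation limit is the looser one |
| FiO2 | < 40 mmHg | < 30 cmH2O | units differ; not comparable |

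Only RR clearly has to reach a lower limit. The PEEP and FiO2 entries must be reconciled between the two lists before any distance from extubation can be read from them. Separately, Section 3.3.3 names oxygen requirements among the factors that help determine extubation success. Starting status is therefore plausibly prognostic, but the documents do not quantify it.

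**2. The plan's own sample size.** Section 7.3.1: "Accepting an alpha risk of 0.05 and a beta risk of 0.2 in a two-sided test"; "A proportion in one of both groups has been estimated to be 16" per cent; "a difference greater than or equal to 0.1 percent units", read as 10 percentage points; "It has been anticipated a drop-out rate of 5% (0,05"). With the arcsine formula, h = 2·asin√0.26 − 2·asin√0.16 = 0.2471 and n = 2·((1.960 + 0.842)/h)² = 257.1. Then 257.1/0.95 = 270.6, or 271 per arm, as stated. (The pooled normal formula gives 260, or 274 after drop-out.) This figure concerns reintubation and is not affected by the present point.

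**3. Reference case for weaning time (assumed).** The plan states no hazard ratio, event count or power for this endpoint. After 5% loss, 271 × 0.95 ≈ 257 per arm, or 514 infants, all assumed to be extubated with no censoring. Schoenfeld's formula gives 80% power at HR = exp(2 × (1.960 + 0.842)/√514) = 1.28. For scale, 514 events give 54% power at HR 1.20, 72% at 1.25 and 84% at 1.30.

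**4. Simulation.** Exponential times, treatment HR 1.28, and one standard-normal starting score with log-hazard b per SD. Its share of the variance in log time is b²/(b² + π²/6). Each scenario has 2,000 trials, with a Monte Carlo standard error of about 1 point (√(0.8 × 0.2/2000) = 0.009).

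| HR per SD (b) | Share of log-time variance | Power, arm only | Power, arm + score | Loss, points | Mean HR, arm only |
|---|---|---|---|---|---|
| 1.00 (0) | 0% | 78% | 78% | 0 | 1.28 |
| 1.22 (0.2) | 2% | 77% | 80% | 3 | 1.27 |
| 1.35 (0.3) | 5% | 73% | 80% | 6 | 1.26 |
| 1.65 (0.5) | 13% | 66% | 80% | 14 | 1.23 |
| 2.01 (0.7) | 23% | 56% | 80% | 24 | 1.21 |

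Losses are taken from unrounded powers. With the score in the model, the mean HR is 1.28 to 1.29 throughout.

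**5. Closer to the planned model.** The planned Cox model already holds gestational-age class and birthweight. Adding a proxy correlated 0.3, 0.5 or 0.7 with the score (1,000 trials each) gives:

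- HR 1.65 per SD: power 67%, 67%, 70% with the proxy only, against 79% with the score added. The loss is 9 to 12 points.
- HR 2.01 per SD: power 55%, 64%, 66% (from 54.8, 63.5, 65.5), against 78%, 82%, 78%. The loss is 13 to 23 points.

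Proxies recover part of the loss in most cases and little of it when the correlation is low.

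**6. Cost in model size.** Twenty covariates, with two terms for Apgar, plus arm make 22 parameters. Adding FiO2, PEEP, RR and age as linear terms makes 26. Events per parameter go from 514/22 = 23.4 to 514/26 = 19.8.

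**The case against.** The strongest reply is that the size is entirely assumed. That stands: HR 1.28 was chosen because it gives 80% power, and no document states how strongly the settings predict weaning time. Infants enter only once all four settings are under a cap, which narrows their spread. Extubation also depends on blood gases, infection, the ductus and airway competence, and any of these may be the last criterion met. The true loss could be nil.

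Four stronger readings are tempting and should not be drawn.

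- *The settings drive weaning time by construction.* PIP has the same limit at both points, and the printed PEEP and FiO2 units do not support a stricter limit at extubation. Only RR does.
- *The treatment effect would be biased.* Randomisation protects the comparison. The smaller hazard ratio reflects non-collapsibility: the less adjusted ratio is a valid but different quantity.
- *There is no check that the arms are alike.* Sections 8.1 and 8.2 do compare the listed covariates by protocol; what is missing is the rows for starting status.
- *The values are lost.* Section 10.3 says, in describing follow-up, that clinical data will be in the medical record, so they may be retrievable. Using them later without prespecification would be post hoc.

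None of this removes the gap. If the settings prove uninformative, adjustment costs almost nothing (78% power either way in the first row of the simulation table).

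**Conclusion.** The point holds as a cheap gain in precision on a secondary endpoint. It does not threaten validity, and it leaves the primary sample size of 542 unchanged. The gap is a matter of fact: settings checked at randomisation, and age at that moment, are in neither Table 4 nor Annex 7, so the Cox model cannot use them. The size rests on assumptions: 514 uncensored extubations, HR 1.28, and a prognostic strength between none and 2.01 per SD. On those terms the loss is 0, 3, 14 or 24 points of power for no, weak, moderate or strong prognostic value against an arm-only model, and in most cases somewhat less with the planned covariates as proxies. A reader might take the lower end of that power range as a forecast; the documents do not support any single value in it.

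**What to change.** 1. Add FiO2, PEEP, RR, PIP and postnatal age in days, all at randomisation, to Table 4 and Annex 7.
2. Prespecify in Section 8.3 that the Cox model for weaning time includes FiO2, PEEP, RR and age at randomisation, or one defined summary of them. PIP can be recorded for description only, since its limit does not change.
3. Add the five items to the comparison by arm in Sections 8.1 and 8.2.
4. Reconcile the units of PEEP and FiO2 between the weaning-start and extubation lists in Section 7.5, so that the new fields are recorded on one scale.

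The cost is five fields per infant, a few more model parameters and a sentence in the analysis plan; no extra patients or procedures are needed. Dropping obstetric-history items, or adding settings to the reintubation model, is optional and not supported by any calculation here.

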7.5 Study intervention

In this study there will be two different protocols applied for weaning of invasive mechanical ventilation in extremely and very preterm newborns with NRDS: PSV and ACVGV. These protocols will be applied by professional neonatologists.

When an extremely or very preterm newborn is in invasive mechanical ventilation due to NRDS and meets all inclusion criteria and any exclusion criteria, an informative document (see Annex 4) and an informed consent (see Annex 5) will be given to the parents or legal guardians to sign.

Once the newborn enters the study, the neonatologists will wait until this patient meets the **criteria to start the weaning**. These criteria will be **precisely explained** in the document given to all hospital coordinators during the formation sessions. The weaning criteria are the following:

- Clinical criteria:
 - o Stable patient
 - o No intercurrent process that may hinder weaning

- Respirator parameters
 - o $FiO_2 < 40$ mmHg
 - o $PEEP < 7$ cmH₂O
 - o $RR < 50$ rpm
 - o $PIP < 20$ cmH₂O

When the patient meets the weaning criteria, the intervention will start. The intervention will be carried out by a neonatology expert. The patient will be randomly assigned in one of the two groups:

- o Group 1: The protocol used for the weaning will be **pressure support ventilation (PSV)**

- o Group 2: The protocol used for the weaning will be **assist control volume guarantee ventilation (ACVGV)**

Both protocols of weaning have been properly explained in section 3.3.3 *Invasive mechanical ventilation*.

The patient will remain in weaning until he or she meets the **criteria for extubation**. These criteria will be **precisely explained** in the document given to all hospital coordinators during the formation sessions. The patient will be extubated to a CPAP with a nasal PEEP of 6 mmHg. The extubation criteria are the following:

- Gasometrical criteria:
 - o pH > 7,3
 - o pCO₂ < 50 mmHg
 - o pO₂ > 70 mmHg
 - o Sat Hb 90-95% (haemoglobin saturation)

- Clinical criteria:
 - o Stable patient
 - o Without active infectious process
 - o Without hemodynamically significant ductus
 - o Neurologically capable of maintaining a patent airway

- Respirator parameters:
 - o PEEP < 6 mmHg
 - o FiO₂ < 30 cmH₂O
 - o RR < 20 rpm
 - o PIP < 20 cmH₂O
 - o Tidal volume 5 ml/kg

[figure not shown]
Once the extubation is done, the patient will be **followed up for 72 hours**. If during this follow up the patient meets the **reintubation criteria**, the newborn will be reintubated and this data will be properly collected. These criteria will be **precisely explained** in the document given to all hospital coordinators during the formation sessions. The reintubation criteria are the following:

- Gasometrical criteria:
 - o pH < 7,2
 - o pCO₂ > 60 mmHg
 - o pO₂ < 70 mmHg
 - o Sat Hb < 90% (hemoglobin saturation)

- Clinical criteria:
 - Progressive increase in work of breathing.
 - Frequent apnoeas requiring positive pressure ventilation.

- Respirator parameters in NIV:
 - PEEP > 6 mmHg
 - FiO₂ > 50 cmH₂O

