3.2.6 Delivery room stabilisation

The European Consensus Guidelines on the Management of Respiratory Distress Syndrome, make these **recommendations for stabilization in the labour room** (47):

- **Delay cord clamping for at least 60 seconds**, especially in stable preterm infants.
- Use a **T-piece** device rather than bag and mask.
- Stabilise spontaneously breathing preterm infants with **CPAP**. If apnoeic, start mask ventilation/inflations with an initial CPAP pressure of 6–8 cm H₂O and peak inspiratory pressures of 20-25 cm H₂O.
- Oxygen for resuscitation should be controlled using a blender. Start with FiO₂ of 0.30 for babies <28 weeks, 0.21–0.30 for those 28–31 weeks, and 0.21 for 32 weeks and older. Adjust FiO₂ guided by pulse oximetry, aim for SpO₂ of 80% or more by 5 minutes of age.
- Intubation should be reserved for babies who do not respond to positive pressure ventilation via face mask or nasal prongs.
- **Plastic bags or occlusive dressings, radiant warmers, and humidified gas** should be used during stabilisation for babies <32 weeks of gestation to reduce the risk of hypothermia.

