3.2.8 Treatment

The aim of modern RDS management is to **maximize survival** while **minimizing complications**.

Oxygen supplementation over stabilization

In preterm babies receiving oxygen, the **target saturation should be between 90% and 94%**, so the alarm thresholds should be set at 89% and 95%.

Due to the high risk of having retinopathy of prematurity (ROP) in preterm infants, it is important to have protocols for screening and treating preterm babies for ROP.(47)

Surfactant administration

Surfactant is not administered to all newborns with RDS. If it is administered, it should be given early in the course of the disease. These are the **criteria recommended for surfactant administration** by the European Consensus Guidelines on the Management of Respiratory Distress Syndrome (47):

- Preterm babies < 30 weeks of gestation requiring intubation for stabilization.
- Worsening babies with RDS if $FiO_2 > 0.30$ on CPAP pressure ≥ 6 cm H₂O or if lung ultrasound suggests surfactant requirement.
- A second and occasionally a third dose of surfactant should be given if there is persistent evidence of RDS, such as persistent high oxygen requirements and other problems have been excluded.

It is recommended the use of natural surfactant given by LISA technique (less invasive surfactant administration) when the baby is on CPAP. The LISA technique uses a thin catheter for surfactant administration, and completely avoids “bagging”, allowing the infant to maintain spontaneous breathing on CPAP while surfactant is gradually delivered in small aliquots.

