3.3 Mechanical ventilation

3.3.1 Concepts

Mechanical ventilation can be delivered to the patient by invasive or non-invasive methods. There are some variables that need to be considered for effective implementation of mechanical ventilation, which are more important and more commonly used in invasive ventilation. (49)

- **Tidal volume:** is the volume of air delivered to the lungs by the ventilator with each breath. It is measured in millilitres.
- **Respiratory rate:** is set according to the desired minute ventilation.
- **Minute ventilation:** is the product of the respiratory rate and the tidal volume. It is expressed in litres per minute. It is important to provide an adequate minute ventilation to allow the patient to compensate for metabolic demands.
- **PEEP (Positive end-expiratory pressure):** is the pressure in the alveoli above atmospheric pressure at the end of expiration. The PEEP delivered by mechanical ventilation allows the delivery of positive pressure at the end of expiration to prevent the unstable lung units from collapsing. It is measured in cmH₂O.
- **FiO₂** (Fraction of inspired oxygen)
- **PIP (Peak inspiratory pressure):** Peak airway pressure is a measure of the maximum pressure felt by the airways during inspiration. In the passive patient, peak pressure, depends on the respiratory rate, tidal volume, and inspiratory flow rate in volume-cycled modes of mechanical ventilation. In the awake and active patient, the patient's effort contributes to the peak pressure. It is measured in cmH₂O.
- **Flow rate:** is the maximum flow at which a set tidal volume of breath is delivered by a ventilator.

- **Plateau pressure:** is the pressure that is applied by the mechanical ventilator to the small airways and alveoli. Plateau pressure is measured at the end of inspiration.

We can talk about two different types of mechanical ventilation, the **non-invasive**, where there is no endotracheal intubation; and the **invasive**, where there is endotracheal intubation.

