Proposed Criteria for Failure During 2 Hours on CPAP < 5 cmH₂O or T-piece

Clinical Criteria:

- Diaphoresis
- Nasal flaring
- Increasing respiratory effort
- Tachycardia (increase in HR > 40 bpm)
- Cardiac arrhythmias
- Hypotension
- Apnea

Laboratory Criteria:

- Increase of PETCO₂ > 10 mmHg
- Decrease of arterial pH < 7.32
- Decline in arterial pH > 0.07
- PaO₂ < 60mmHg with an FiO₂ > 0.40 (P/F O₂ ratio < 150)
- SpO₂ declines > 5%

Table 3 - Criteria for extubation Readiness Test Failure (56)

Invasive mechanical ventilation in RDS

Despite best efforts to maintain as many preterm babies as possible on NIV, approximately **half of babies < 28 weeks will require invasive mechanical ventilation.** (57)

The aim of invasive mechanical ventilation is to achieve “acceptable” blood gases by ventilating at optimal lung volumes (while avoiding overdistension and atelectasis).

The initial tidal volume is usually set at around 5 ml/kg (58) with a maximum PIP of 25-30 cmH₂O. Adjustments to the initial tidal volume have to be done, according to assessment of work of breathing and blood gas evolution. Required tidal volumes vary around 5-7 ml/kg, the range tending to increase with increasing postnatal age.

PEEP should be adjusted to keep the lung open by finding a point where FiO₂ is at its lowest with haemodynamic stability and acceptable blood gases.

Once stabilised on invasive mechanical ventilation and with evidence of spontaneous respiratory effort, clinicians should immediately start planning for weaning to NIV. Some infants require a very short period of ventilation, particularly those with RDS following surfactant therapy, and early extubation of even the smallest babies who achieve low ventilator settings should be encouraged. (47)

Infant's size, absence of growth restriction, oxygen requirements and blood gases can all help to determine the success of extubation. (59) Delaying extubation does not improve the chances of success.

When weaning from invasive mechanical ventilation, it is reasonable to tolerate a modest degree of hypercarbia, provided the pH remains above 7.22.

Caffeine (20 mg/kg loading, 5-10 mg/kg maintenance) should be used to facilitate weaning from MV.(60)

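### Section 7.5 prints six of its 12 ventilator or CPAP values with a wrong or inconsistent unit: FiO2 three times as a pressure, PEEP or CPAP three times in mmHg instead of cmH2O.

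*Combined protocol and SAP*

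**What the plan says.** Section 7.5 lists four ventilator values to start weaning, five for extubation, one CPAP level after extubation and two limits on non-invasive support for reintubation.

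- **FiO2.** The weaning-start limit is below 40 mmHg, the extubation limit is "FiO₂ < 30 cmH₂O" and the reintubation limit is "FiO₂ > 50 cmH₂O".
- **PEEP and CPAP.** Weaning starts at PEEP below 7 cmH2O. The extubation limit is below 6 mmHg and the reintubation limit is above 6 mmHg. For the support given in between: "The patient will be extubated to a CPAP with a nasal PEEP of 6 mmHg".
- **Consequence of meeting the reintubation criteria.** "the newborn will be reintubated and this data will be properly collected".

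Elsewhere the protocol uses other units. Section 3.3.1 expands FiO2 as a fraction and says of PEEP that it serves to "prevent the unstable lung units from collapsing. It is measured in cmH₂O". Section 3.2.6 gives starting oxygen as a fraction, down to "0.21 for 32 weeks and older". The readiness-test criteria in section 3.3.3 have "PaO₂ < 60mmHg with an FiO₂ > 0.40". Section 3.2.8 puts FiO2 as a fraction and CPAP in cmH2O on one line, and section 3.3.2 gives a CPAP starting pressure of about 6 to 8 cmH2O.

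Section 7.5 says that a document for the hospital coordinators will explain the criteria precisely. Section 10.3, stage 2, describes it: agreed ventilator values for starting weaning and for extubation, plus clinical and blood-gas criteria for weaning, extubation and reintubation.

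**The concern.** These are operating thresholds, not background text. They determine when the randomised mode begins, when the tube comes out, what support follows and when it goes back in. They therefore bound both outcomes in section 7.4: reintubation within 72 hours of extubation, and time from the start of weaning to extubation.

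The two kinds of error differ. A pressure unit on FiO2 is dimensionally impossible, so the reader knows at once that it is a slip. A PEEP or CPAP in mmHg is a valid quantity that gives a believable number, so it does not announce itself as an error. The second kind could be followed literally, and at reintubation the literal and the intended limits classify some infants differently.

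**Working it through.** The plan has no figure of its own to reproduce here. The check is a count, followed by unit conversion.

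**Step 1: count.** All values are from section 7.5. Blood-gas values are left out, because mmHg is correct for them.

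| Decision | Value as printed | Unit |
|---|---|---|
| Weaning start | FiO2 < 40 mmHg | wrong |
| Weaning start | PEEP < 7 cmH2O | correct |
| Weaning start | RR < 50 rpm | acceptable |
| Weaning start | PIP < 20 cmH2O | correct |
| Extubation | PEEP < 6 mmHg | inconsistent |
| Extubation | FiO2 < 30 cmH2O | wrong |
| Extubation | RR < 20 rpm | acceptable |
| Extubation | PIP < 20 cmH2O | correct |
| Extubation | tidal volume 5 ml/kg | correct |
| After extubation | CPAP 6 mmHg | inconsistent |
| Reintubation | PEEP > 6 mmHg | inconsistent |
| Reintubation | FiO2 > 50 cmH2O | wrong |

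Total: 4 + 5 + 1 + 2 = 12. Affected: 3 FiO2 + 2 PEEP + 1 CPAP = 6.

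**Step 2: PEEP and CPAP taken literally.** The conversion is 1 mmHg = 1.3595 cmH2O.

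- 6 × 1.3595 = 8.16 cmH2O.
- Against 6 cmH2O: 8.16 / 6 = 1.36, so 36% higher.
- Against the weaning-start limit: 8.16 − 7 = 1.16 cmH2O. The extubation limit would be looser than the limit the infant had already met to begin weaning, which is the wrong order.
- At reintubation, an infant on 7 or 8 cmH2O exceeds a limit of 6 cmH2O but not one of 8.16 cmH2O. Both levels lie within the 6 to 8 cmH2O starting range of section 3.3.2.

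**Step 3: FiO2 taken literally.** The only way to give the printed units a meaning is to treat them as oxygen partial pressures. This assumes a total pressure of 760 mmHg (range 700 to 760).

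- The lowest FiO2 the protocol mentions is 0.21: 0.21 × 760 = 159.6 mmHg, or 159.6 × 1.3595 = 217 cmH2O. At 700 mmHg it is 147 mmHg, or 200 cmH2O.
- Weaning start: 40 / 760 = 0.053 (0.057 at 700).
- Extubation: 30 / 1.3595 = 22.1 mmHg; 22.1 / 760 = 0.029 (0.032 at 700).
- Reintubation: 50 / 1.3595 = 36.8 mmHg; 36.8 / 760 = 0.048 (0.053 at 700).

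All three are far below 0.21. The two upper limits could never be met and the reintubation limit would always be exceeded. No one would act on this reading. The step shows only that the labels must be errors.

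**The case against.** The strongest reply is that this is an editorial slip that corrects itself. The users are neonatologists. The protocol's own definitions point to FiO2 in percent and PEEP in cmH2O, and an FiO2 of 40 has no plausible meaning other than 40%. Most of this stands: the intended values can largely be inferred. It is weaker for PEEP and CPAP, because 8.16 cmH2O lies just above the protocol's own starting range and does not look absurd.

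The second reply is that the site document is planned for the training sessions in April 2024, before recruitment opens in May, and will give agreed ventilator values. This also carries weight, and it rules out saying that staff will have to work from inference alone. But the document is not in the file, so whether it corrects the units is unknown. Section 10.3 describes its ventilator values as those for weaning start and extubation. For reintubation it names only clinical and blood-gas criteria, so the two limits on non-invasive support are not clearly covered.

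A reader might infer that all six values are unusable as printed. That is true only of the three FiO2 limits. The three mmHg values can be set on a device; their fault is conflict with the protocol's own unit and with its weaning-start limit.

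**Conclusion.** The point holds as an error in the text at decision thresholds. Six of 12 values are affected: three FiO2 limits are dimensionally impossible, and three PEEP or CPAP values are in a unit inconsistent with the rest of the protocol. The practical size is the gap between 6 and 8.16 cmH2O, which reverses the order of the weaning-start and extubation limits and reclassifies infants on CPAP of 7 or 8 cmH2O against the reintubation limit.

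A reader might go further and infer a bias between the arms, a shift in the reintubation rate or a need for a different sample size. The documents support none of these. The same thresholds apply to both arms, section 7.3.4 randomises the patients of each hospital, and nothing in the file gives the distribution of CPAP levels or says how the reintubation criteria combine. Any effect on the event rate cannot be derived.

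The conclusion rests on the pressure conversion, on the protocol's own definitions and on the units being plain list text and one sentence, where text extraction is an unlikely cause. The corrected values are inferred and need clinical confirmation.

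**What to change.** Before first enrolment, restate the values in section 7.5:

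- FiO2 as a fraction: below 0.40 to start weaning, below 0.30 for extubation, above 0.50 for reintubation.
- PEEP and CPAP in cmH2O: below 7 to start weaning (unchanged), below 6 for extubation, 6 for CPAP after extubation, above 6 for reintubation.

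Have the clinical leads confirm each number as well as its unit, since the intended values are not printed anywhere. Carry the confirmed set into the site document described in section 10.3, and state there that it includes the PEEP and FiO2 limits on non-invasive support for reintubation.

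The cost is an edit to one section and to a training document not due until the training sessions. It needs no additional patients or procedures.
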